8.2.2. Treatment Compliance

Study product compliance during the 28-week treatment period will be calculated for each subject by whether a subject takes all doses of study product as instructed. The number of capsules taken will be calculated by subtracting the number of capsules returned from the number of capsules dispensed during the treatment period.

The study product compliance (%) will be calculated by dividing the total number of capsules taken by the total number of capsules prescribed and then multiplying by 100. For calculations of compliance, the number of capsules prescribed will be adjusted downward if the subject was instructed not to take study capsules on certain days. Reduced dosing after Visit 8 will be excluded from the compliance calculation and summary. The formula below will be used.

Compliance (%) = [(number of capsules dispensed – number of capsules returned) / (number of days in study for which capsules were prescribed x number of capsules prescribed per day)] x 100

Study product compliance will be presented in a listing by individual and treatment cohort, with compliance presented as continuous variable. A subject will be considered compliant if the study product compliance is $\geq 80\%$ to $\leq 120\%$ of prescribed dose.

The overall study product compliance will be summarized by treatment cohorts and combined lenabasum cohort, with compliance presented as a continuous variable and as number of subjects and percentage of subjects in different categories of compliance ($< 80\%$, $80 - 120\%$, $> 120\%$), for Visits 2-8.

9. EFFICACY ANALYSES

All efficacy variables will be summarized descriptively by treatment and scheduled visit as applicable using the mITT population. Unscheduled visits including unscheduled Possible PEx visits will be excluded from the efficacy by visit analyses, unless otherwise specified for these visits.

9.1. Handling of Missing Data

Missing data will not be imputed for efficacy and safety analyses unless specified otherwise. See [Section 4.1.14](#) for handling data during COVID-19 pandemic.

If start or end date of antibiotics is incomplete:

- Missing start day only: If month and year are the same as first dose date of study product, impute the antibiotics start date using first dose date of study product, impute the missing day using '01'
- Missing start day and month, but year not missing: If year is the same as first dose date of study product, impute the antibiotics start date using first dose date of study product. If year is not the same as first dose date, impute the missing day using '01' and the missing month using 'Jan'
- Start date missing completely: impute the missing date using first dose date of study product
- Missing end day only: impute the missing end day using the last day of the month
- Missing end day and month, but year not missing: impute the missing day using '31' and missing month using 'Dec'
- Missing end date completely: impute using last visit date

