4.2. Study Efficacy Endpoints

4.2.1. Primary Efficacy Endpoint

The primary efficacy endpoint is the event rate of new PEx per subject per 28 weeks using the primary definition of new PEx comparing the lenabasum 20 mg BID and placebo cohorts. The event rate is based on the occurrence of new PEx, and the occurrence will be assessed during the treatment phase. It is defined as follows:

The primary endpoint will be calculated by the following for each treatment cohort:

Event rate of PEx (per subject-28 Weeks) for a treatment group is calculated as follows:

Total number of PEx using primary definition during the treatment period / [sum of subject treatment exposure durations in the treatment group (days) / 196]

[figure not shown]
Event rate of PEx (per subject) for a treatment group (without adjustment of treatment exposure) is calculated as follows:

Total number of PEx using primary definition during the treatment period / number of subjects in the treatment group

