5.1.1. Primary Definition of New Pulmonary Exacerbation

The derivation for new PEx by the primary definition is provided below. The rules for defining new antibiotics used for new PEx, including the start and stop days, are also provided below.

Primary definition of new PEx:

- Physician diagnosis of PEx
- Prescription of new antibiotics for PEx
- Start date of new antibiotics for PEx is > 28 days after the stop date of any antibiotics given for any previous PEx. The physician does not need to determine if there is > 28 days from last use of antibiotics to the new antibiotics for PEx analysis purposes. The > 28-day gap will be determined centrally
- A new PEx is not defined by the number of antibiotics prescribed or the order or route of administration of the antibiotics (oral or IV) for that new PEx
- ≥ 4 out of 12 Fuchs criteria are met

New antibiotics for PEx

- Must be given for PEx

- Must be administered by oral or IV route
- Start date is day the physician prescribes that the subject should take this antibiotic treatment for a PEx
- Stop date is the last day the physician prescribes that the subject should take this antibiotic treatment for a PEx
- Start day > Day 1
- Start day \leq Day of Visit 8 or discontinuation from the study
- Regularly given prophylactic inhaled, oral, or IV antibiotics do not count as new antibiotics unless the dose is increased or given early for a PEx

Start day of a new PEx:

The first day that the physician prescribes that the subject should take any new antibiotic treatment for that new PEx

Stop day of a new PEx:

The last day that the physician prescribes that the subject should take any new antibiotic treatment for that new PEx or day of discontinuation from the study, whichever is sooner

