5.2. Secondary Efficacy Endpoints

5.2.1. Secondary Definition of Pulmonary Exacerbation

The following derivation is provided for new PEx by the secondary definition. Definitions of new antibiotics for PEx and start and stop days of new PEx are as outlined in [Section 5.1.1](#).

Secondary definition of new PEx:

- Physician diagnosis of PEx
- Prescription of new antibiotics for PEx
- Start date of new antibiotics for PEx is $>$ 28 days after the stop date of any antibiotics given for any previous PEx
- A new PEx is not defined by the number of antibiotics prescribed or the order of route of administration of the antibiotics (oral or IV) for that new PEx

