6. GENERAL STATISTICAL CONSIDERATIONS

6.1. Reporting Conventions

All data analysis will be performed by Statistics & Data Corporation after the study is completed and the database has been locked. The following reporting conventions will be used:

- Outputs will be provided in rich text format for tables and portable document format for tables, listings, and figures using landscape orientation.
- Data from all study centers will be combined for analysis.

- All study data will be listed by subject, treatment, and visit (as applicable) based on all randomized subjects unless otherwise specified. Additional data listings will be provided as described in the sections for the data analyses.
- Summaries for continuous and ordinal variables will include: the number of observations (n) of observations, arithmetic mean, standard deviation (SD), median, minimum (min), maximum (max). Unless specified in the actual table shells, the mean, median, first quartile, second quartile, third quartile, (interquartile range), the upper and lower limits of the confidence interval (CI) will be displayed to one more decimal place than the original data (derived analysis data). Standard deviation and standard error values will be displayed to two more decimal places than the original data. Minima and maxima will be displayed to the same number of decimal places as the original data. Summaries for discrete variables will include frequency counts and percentages. All percentages will be rounded to one decimal place (i.e., XX.X%).
- The number and percentage of responses will be presented in the form XX (XX.X%), where the percentage is in parentheses. The denominator of all percentages will be number of subjects in the analysis population, unless otherwise stated. When count data are presented, the percent will be suppressed when the count is zero in order to draw attention to the non-zero counts. A row denoted “Missing” will be included in count tabulations where necessary to account for dropouts and missing values. Non-zero percentages will be rounded to one decimal place, except 100% will be displayed without any decimal places.
- The day of the first dose of study product will be defined as Day 1, which is the day of Visit 1. All study days before Day 1 will be calculated as (assessment date – first dose date of study product). The study day on or post Day 1 will be calculated as (assessment date - first dose date of study product + 1).

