9.4. Primary Efficacy Analysis

9.4.1. Event Rate of New Pulmonary Exacerbations per Subject per 28 Weeks by Primary Definition

The primary efficacy endpoint is the event rate of new PEx per subject per 28 weeks using the primary definition (Sections [4.2.1](#) and [5.1](#)), for the comparison of lenabasum 20 mg BID cohort to the placebo cohort, in the mITT population, through Visit 8 (Week 28) which is the treatment period.

The event rate per subject per 28 weeks of new PEx will be compared between the lenabasum and placebo cohorts using a Poisson regression model with effects of treatment and log (subject treatment exposure duration), adjusting for baseline subject characteristics of site location (United States; other countries), number of new PEx requiring IV antibiotics in the previous year (1; 2; 3); FEV1 % predicted (< 70; \geq 70); and baseline CFTR-targeting medications use (Yes; No – taken concomitantly on Day 1, baseline), and based on the mITT population.

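### Section 9.1 sets three kinds of incomplete antibiotic start date to Day 1, which Section 5.1.1 does not accept, so a PEx dated only in that way is not counted

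*SAP*

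**What the plan says.** Section 9.1 of the SAP gives the rules for incomplete antibiotic dates. Three of them return the first-dose date:

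- Whole date missing: "Start date missing completely: impute the missing date using first dose date of study product".
- Day and month missing: "If year is the same as first dose date of study product, impute the antibiotics start date using first dose date of study product".
- Day missing: "If month and year are the same as first dose date of study product, impute the antibiotics start date using first dose date". The same bullet then gives '01' as the day, with no 'otherwise' between the two instructions. I read '01' as the branch for any other month.

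Section 6.1 fixes the study-day scale: "The day of the first dose of study product will be defined as Day 1".

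Section 5.1.1 lists the conditions for a new antibiotic for PEx, one of which is "Start day > Day 1". The primary definition requires such an antibiotic. The secondary definition in Section 5.2.1 requires it too and borrows the conditions: "Definitions of new antibiotics for PEx and start and stop days of new PEx are as outlined in" Section 5.1.1.

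In Section 4.2.1 the denominator of the event rate is the "sum of subject treatment exposure durations in the treatment group (days) / 196". It depends on exposure only, not on whether an event was accepted.

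**The concern.** The antibiotic start date decides whether a PEx exists for analysis and when it began. An imputation rule for that date should allow a real event to be counted. Here the default value is the one day that the endpoint definition rules out by a strict inequality.

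The event at risk is one that a physician diagnosed and recorded after Day 1, with all other criteria met, but whose only antibiotic record has a start date of one of the three kinds. It becomes a non-event because of a gap in a date field.

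It is lost from the primary endpoint and from the first seven secondary endpoints in Section 4.2.2 (event rate and time to first PEx, both definitions, both doses). The subject's exposure stays in the rate denominator and in the Poisson model of Section 9.4.1. In the time-to-event analysis of Section 9.5.3 the subject is either treated as event-free or given a later first event.

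**Working it through.** **1. The rules side by side.** Study day on or after first dose = date − first-dose date + 1 (Section 6.1). The first-dose date itself gives 0 + 1 = Day 1.

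| Start date as recorded | Imputed by 9.1 | After Day 1? |
|---|---|---|
| Wholly missing | First-dose date, Day 1 | No |
| Year only, same year as first dose | First-dose date, Day 1 | No |
| Day missing, first-dose month | First-dose date, Day 1 | No |
| Day missing, later month | First of that month | Yes |
| Year only, later year | 1 January of that year | Yes |

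The first three fail by construction. If the '01' instruction is taken literally for the first-dose month, the result is on or before Day 1 and fails as well. I found no passage that exempts imputed dates or substitutes a visit date. A PEx with a second antibiotic record adequately dated after Day 1 still counts.

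**2. How far each rule reaches, given that a date is incomplete in that way.** Eligible on-study starts run from Day 2 to Day 196, which is 195 days.

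- Wholly missing: 195/195 = 100%.
- Year only: the share of those days in the first-dose calendar year. This is 100% for first doses up to 19 June, 107/195 = 55% for 15 September and 30/195 = 15% for 1 December. The mean is 73% if first doses are spread evenly over a year (my assumption).
- Day missing: mean 7.5% on the same assumption, at most 30/195 = 15%.

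These are shares of possible start days, conditional on an incomplete date. They are not shares of PEx events.

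**3. What an assumed loss would cost.** First, the plan's own figure. Section 6.3 states 80% power with a control rate of 0.80, a rate ratio of 0.65 and 166 per arm allowing for about 15% dropout. With 166 × 0.85 = 141 per arm:

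- Expected events: placebo 141 × 0.80 = 112.8; lenabasum 20 mg 141 × 0.52 = 73.3; total about 186.
- Power = Φ(|ln 0.65| / √(1/112.8 + 1/73.3) − 1.96) = Φ(0.4308/0.1500 − 1.96) = Φ(0.91) = 81.9%, close to the stated 80%.

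Multiplying the events in both arms by (1 − loss):

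| Assumed loss, both arms | Events lost | Power, 141 per arm |
|---|---|---|
| 0 | 0 | 81.9% |
| 1% | 1.9 | 81.5% |
| 2% | 3.7 | 81.1% |
| 5% | 9.3 | 79.9% |
| 10% | 18.6 | 77.8% |

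The rate ratio does not change: at 5% loss, 0.80 becomes 0.76 and 0.52 becomes 0.494, and 0.494/0.76 = 0.65. The loss percentages are illustrations only.

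**The case against.** **Nothing in the SAP shows an affected record.** Section 4.1.3 anticipates prescriptions from outside physicians, but sends those subjects to a Possible PEx Visit where the investigator completes the AUR-Q, a process meant to capture the course. Whether the case report form accepts a partial start date cannot be seen. This stands. The conflict between the rules is certain; its frequency is not known.

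**The COVID-19 period.** A reader might infer from Table 1, which moves PEx information to phone or computer interviews, that many dates will fall into the trap. The SAP's own dates do not support that. Section 4.1.14 says that all subjects had completed Week 16 when restrictions began in mid-March 2020. Counting back 112 days from 16 March 2020 gives 25 November 2019, or 9 December with a two-week visit window. First doses were thus no later than 2019. A course begun in the interview period with its year known is dated 1 January 2020 or later, which is after Day 1, so only a wholly missing date would trigger the problem. The same section reports that all but 1 of the 67 subjects still short of Visit 8 had PEx assessments.

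**Power.** A reader might also infer that the trial falls below 80% power. That needs an assumed loss near 5% and an n of completers only. The primary analysis is mITT with exposure in the model, so dropouts contribute. If they contribute half their exposure (an assumption), the effective n is 166 × 0.925 = 153.5 per arm, and the same formula gives 85.0% with no loss, 83.2% at 5% and 81.1% at 10%.

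**Bias.** The documents give no reason why incomplete dates should be more common in one arm of a blinded trial, so a biased treatment comparison cannot be claimed.

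**Risks of a replacement rule.** Dating a course from the visit could place its start after its end, or stretch the gap from an earlier course past 28 days and turn a continuation into a new PEx. Both points are sound, and the fix has to provide for them.

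**Conclusion.** The point holds in a narrow form. Sections 9.1, 6.1 and 5.1.1, with 5.2.1 by reference, are inconsistent: three kinds of incomplete start date are sent to a day that the endpoint definition excludes, with no exemption. Followed as written, the plan turns a PEx supported only by such a record into a non-event for the primary endpoint and seven secondary endpoints.

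The size is unknown, because the SAP gives no frequency of incomplete dates. It is probably small and may be nil. If losses are proportionally equal in the arms, the reported rates are too low and power falls slightly (under one percentage point for a 1 to 2% loss), but the rate ratio is not biased. The point should be corrected because the error is certain where it applies, bears on the primary endpoint and is cheap to remove. It is not evidence that the trial's result would change.

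**What to change.** Amend Section 9.1 before unblinding. Section 2 bars sponsor changes once the SAP is signed, so the change is best made before signature.

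- For antibiotics recorded for a PEx first reported after Day 1, do not use the first-dose default unless the record shows that the course began on or before Day 1.
- For these records, impute the start from the date of the AUR-Q or Possible PEx Visit at which that PEx was recorded. Keep it within any known month and year, after Day 1, and no later than any known stop date of the course.
- Decide in blinded review whether an affected record continues an earlier course, so that a late imputed start does not by itself satisfy the 28-day gap.
- Keep the present rule for all other courses, and add the missing 'otherwise' to the day-missing bullet.
- Report the number of affected records, and repeat the PEx analyses under the present rule as a sensitivity analysis.

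The cost is a few sentences, minor derivation code and a short blinded listing, using visit dates already collected. The drawback is that the onset of affected events is approximate, which carries into time to first PEx and the gap rule.

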4.1.4. Study Population and Background Treatment for CF

The study population is males and females with CF \geq 12 years of age with FEV1 \geq 40% predicted and $<$ 100% predicted at least once within 12 months before Screening. Subjects must have 2 to 3 new PEx treated with IV antibiotic therapy within 12 months before Screening or, as an alternative, 1 new PEx treated with IV antibiotics and at least 1 PEx treated with oral antibiotics within 12 months before Screening.

Subjects should be considered stable and on stable medication for treatment of CF prior to Visit 1. For example, subjects are allowed use of prophylactic antibiotics and CFTR-modulating medications if they are on stable doses within 28 days of Visit 1. A subject with an increase in dose or initiation of any new chronic therapy for CF within 28 days of Visit 1 is not eligible for enrollment. Changes in treatment of CF after study start are allowed when those changes are in the subject's best medical interest, as assessed by the treating physician. Sensitivity analyses will be performed to assess potential impact of treatment at Baseline with drugs that might reduce rate of PEx, including concomitant CFTR-targeting medications, azithromycin, prophylactic antibiotics, and dornase alfa on the primary and first secondary efficacy outcome.

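### Late imputation of missing antibiotic stop dates, combined with the > 28-day gap rule, removes real later PEx from both event-rate endpoints

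*SAP*

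**What the plan says.** SAP Section 9.1 has three rules for an incomplete antibiotic end date:

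- day missing: "Missing end day only: impute the missing end day using the last day of the month"
- day and month missing: "Missing end day and month, but year not missing: impute the missing day using '31' and missing month using 'Dec"
- everything missing: "Missing end date completely: impute using last visit date"

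Section 5.1.1 makes the stop date decisive for counting. One condition of a new PEx is "Start date of new antibiotics for PEx is > 28 days after the stop date of any antibiotics given for any previous PEx". The site does not judge this: "The > 28-day gap will be determined centrally". The new course must also start no later than Visit 8 or discontinuation. Section 5.2.1 repeats the gap condition for the secondary definition and shares the date rules: "Definitions of new antibiotics for PEx and start and stop days of new PEx are as outlined in" Section 5.1.1.

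Section 5.1.1 defines the antibiotic stop date as the last day for which the physician prescribed the course. Section 9.2 says that for a subject lost to follow-up, the last visit is the last regularly scheduled visit attended.

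**The concern.** The end-date rules may be harmless for listing medications, but here they feed an endpoint derivation. The later the imputed stop of one PEx course, the longer the period in which no further PEx can be counted. A separate PEx with complete dates can then be dropped because a different course had an incomplete record.

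The text shown does not exempt imputed dates from the gap rule and does not cap an imputed stop at the next dated PEx. The sensitivity analyses in Section 9.4.2 vary the model and the population but not the dates. Section 5.1.1 does cap the stop day of a PEx at study discontinuation, but it states no such cap for the antibiotic stop date used in the gap rule. That cap would not help anyway, because the lost PEx lie before discontinuation.

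At stake are the primary endpoint and the event-rate endpoints under the secondary definition. The loss is not even across arms when the drug works, because only subjects with more than one PEx can lose events.

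**Working it through.** **1. What each rule does to an on-study course**

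*Wholly missing.* Take a PEx starting on Day 22 with a 14-day course (assumed), so the true stop is Day 22 + 13 = Day 35. A second PEx starts on Day 134. The true gap is 134 - 35 = 99 days, so the second PEx counts. With the stop missing and the final visit on Day 196, the gap is 134 - 196 = -62 days, so it does not count. No start on or before Visit 8 can fall more than 28 days after a stop placed at Visit 8 or later, so every later PEx in that subject is lost.

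*Year only.* 31 December + 28 days = 28 January, so PEx count again from 29 January.
- Day 1 on 1 March, with a course that year: Day 196 is 12 September, and all later follow-up is blocked.
- Day 1 on 1 October, with an autumn course: 29 January is Day 121, so Days 121-196 remain countable.
- Averaged over uniform calendar start dates, with 14-day courses and a first PEx on Days 2-154, the block covers all remaining follow-up in about 79% of cases and about 86% of the remaining at-risk time.

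*Day only.* The shift is at most 30 days (first to last day of a 31-day month).

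*Lost to follow-up.* Under Section 9.2 the last visit can precede the start of the course. The imputed stop then falls before the start, and that course blocks nothing. The same rule fails in the opposite direction.

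**2. The plan's own power figure**

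Inputs from Section 6.3: placebo rate 0.80, ratio 0.65 (active rate 0.52), two-sided alpha 0.05, 166 per arm with about 15% dropout, so 166 × 0.85 ≈ 141 per arm.

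SE = √[1/(141 × 0.80) + 1/(141 × 0.52)] = √(0.00887 + 0.01364) = 0.150

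Power = Φ(|ln 0.65|/0.150 - 1.96) = Φ(2.87 - 1.96) = 81.9%

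This agrees with the stated 80% to within 2 points.

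**3. Effect of the wholly-missing rule**

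The check simulates 40,000 subjects per arm over 196 days with the gap rule, calibrated to rates of 0.80 and 0.52. Assumptions not in the SAP: 14-day courses, a share q of stops wholly missing, and either equal subject rates or gamma frailty with shape 1. Power uses the formula above; in the frailty rows it keeps the Poisson standard error.

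| q | Subject rates | Placebo rate | Active rate | Ratio | Power |
|---|---|---|---|---|---|
| 0 | either | 0.800 | 0.520 | 0.650 | 81.9% |
| 5% | equal | 0.789 | 0.516 | 0.654 | 80.4% |
| 10% | equal | 0.779 | 0.512 | 0.657 | 79.1% |
| 20% | equal | 0.758 | 0.503 | 0.664 | 76.3% |
| 5% | frailty | 0.783 | 0.513 | 0.654 | 80.0% |
| 10% | frailty | 0.767 | 0.505 | 0.659 | 78.0% |
| 20% | frailty | 0.734 | 0.490 | 0.668 | 73.9% |

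The drift arises because repeat PEx are commoner on placebo: 17.2% of placebo subjects have two or more, against 7.6% on active (21.2% and 11.1% with frailty).

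As an upper bound, suppose every stop were missing. Each subject then keeps only the first PEx. Events fall by 23.9% on placebo and 15.6% on active (34.8% and 25.4% with frailty), and the ratio becomes 0.72 (0.74).

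The 31 December rule applied to 5-10% of courses gives a ratio of 0.654-0.656 and power of 80.5-79.5% (0.654-0.658 and 80.3-78.6% with frailty).

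**The case against.** The strongest reply is that the effect is small and conservative. The stop date is the last prescribed day, which is knowable when the prescription is written, so missing stops may be rare, and the documents report none. At 5% missing the ratio moves by 0.004. The direction is toward no difference, so the rule does not favour the drug. All of this stands, and it limits the weight of the point. It does not defend the rule, which departs from the SAP's own definition of the stop date and can contradict fully dated later records.

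The suggested replacement also has a cost. A course longer than the median would get too early a stop, and continued treatment of one PEx could be counted as two. That stands too, and is a reason to report both rules.

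Two stronger readings are tempting but not supported.

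- A reader might infer that any late-imputed stop erases all later PEx. That holds only for a wholly missing stop placed at the subject's final visit. The 31 December rule ends on 28 January, and the day-only rule costs at most 30 days.
- A reader might infer that incomplete pre-study courses set a subject's count to zero and distort time to first PEx. The gap rule's reference to any previous PEx has no lower time limit, and entry relies on prior-year events ("Subjects must have 2 to 3 new PEx treated with IV antibiotic therapy within 12 months before Screening", or the alternative in Section 4.1.4). But the SAP does not show that pre-study antibiotic stop dates are collected or imputed under Section 9.1, and its start-date rules, which default to the first dose date, suggest on-study courses. Any such loss would arise from pre-randomisation data, be balanced across arms in expectation, and leave the expected ratio unchanged.

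**Conclusion.** The point holds for on-study courses. Followed as written, Section 9.1 and the gap rule remove genuine, dated PEx from the primary event rate and from the event rates under the secondary definition, and the text shown has no safeguard or sensitivity analysis for it. For subjects lost to follow-up, the same rule can give a stop before the start.

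The bias is toward a ratio of 1. With 5-10% of stops wholly missing it is about 0.004-0.009 on the ratio and about 1.5-4 points of power. These sizes rest on the assumed 14-day courses, the assumed share of missing stops and the planning rates, and the true share is not given.

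Time to first PEx is largely unaffected, because the first on-study PEx is still counted. That would change only if pre-study courses enter the gap rule, which the wording permits but does not establish. This should be corrected, but it does not threaten the trial's conclusion unless missing stops are common.

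**What to change.** In Section 9.1, separate antibiotics given for PEx from the general end-date rules:

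- Impute a missing stop as the course start date plus the median prescribed course length for that route, fixed from blinded pooled data before lock. The result must not be earlier than the start or later than the latest date consistent with the known date parts.
- Use the last visit date only for courses recorded as ongoing.
- State whether pre-study courses enter the gap rule. If they do, cap those not recorded as ongoing at the Screening date.
- Add to Sections 9.4.2 and 9.5.2 a sensitivity analysis under the present latest-date rule. Report by arm how many stops were imputed and how many PEx the gap rule excluded because of an imputed date.

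The cost is a few lines of text and some programming. It needs to be done before signature, since Section 2 allows no sponsor change afterwards. The drawbacks are that the median must be fixed under blind, and that a course longer than the median could be split into two PEx, which the sensitivity analysis would show.
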